3.1.13 Days alive outside of hospital over the course of 28 days

This is defined as the number of days alive outside of hospital from randomization to Day 28 days.

For a day to be counted as outside of hospital, the subject must not be in hospital. If the subject is in hospital but hospitalization is recorded as not clinically indicated, this day will still be considered as a day in hospital and therefore will not be counted in this endpoint.

The following rules will be applied for missing data:

- If a subject withdraws from the study or is lost to follow up on or prior to Day 28, the days with unknown survival/hospitalization status will be considered as follow:
 - If the subject is discharged from hospital when they withdraw from the study or are lost to follow up, days from last known status to Day 28 (or date last known to be alive if death is known, whichever occurs first) will be counted as days alive and outside of hospital.
 - If a subject is in hospital at the time they withdraw from the study, days from last known status to Day 28 will be assumed hospitalized days.

3.1.14 Days alive outside of hospital over the course of 90 days

This is defined as the number of days alive outside of hospital from randomization to Day 90.

For a day to be counted as outside of hospital, the subject must not be in hospital. If the subject is in hospital but hospitalization is recorded as not clinically indicated, this day will still be considered as a day in hospital and therefore will not be counted in this endpoint.

The following rules will be applied for missing data:

- If a subject withdraws from the study or is lost to follow up on or prior to Day 90, the days with unknown survival/hospitalization status will be considered as follow:
 - If the subject is discharged from hospital when they withdraw from the study or are lost to follow up, days from last known status to Day 90 (or date last known to be alive if death is known, whichever occurs first) will be counted as days alive and outside of hospital.
 - If a subject is in hospital at the time they withdraw from the study, days from last known status to Day 90 will be assumed hospitalized days.

3.1.15 Relative change from baseline in oxygenation index

This is defined as the percentage change from baseline in oxygenation index (SpO_2/FiO_2) to Days 3, 5, 7 and 10. For this endpoint, baseline is defined as the observation on the date of randomization (Day 1) only.

Oxygenation index is calculated as

$$SpO_2 [\%] / FiO_2 [\text{decimal}]$$

It will be calculated for the baseline and each post-baseline assessment using the SpO_2 (oxygen saturation) value and the FiO_2 (fraction of inspired oxygen) value collected or derived on the VS and OXYGEN or VENTUSE eCRF pages, respectively. Details on these variables and visit windows are provided in Section 3.2.6 and Section 4.1, respectively.

3.1.16 Time to clinical improvement of at least 2 points (from randomization) on a 9-point category ordinal scale through Day 28

This is defined as the time (in days) from randomization to the date of first demonstrated clinical improvement of at least 2 points (i.e., a decline of two points) on the following 9-point category ordinal scale through Day 28:

0. * Uninfected, no clinical or virological evidence of infection
1. Ambulatory, no limitation of activities
2. Ambulatory, limitation of activities
3. Hospitalized – mild disease, no oxygen therapy
4. Hospitalized – mild disease, oxygen by mask or nasal prongs
5. Hospitalized – severe disease, non-invasive ventilation or high flow oxygen
6. Hospitalised – severe disease, intubation and mechanical ventilation
7. Hospitalized – severe disease, ventilation and additional organ support, such as pressors, renal replacement therapy, extracorporeal membrane oxygenation
8. Death

*Score of zero on 9-point category ordinal scale will not be evaluated in this study.

This information will be collected in the OSCI pages in the eCRF as per the SoA in the CSP.

Baseline ordinal scale score is defined as the result obtained on the date of randomization (Day 1) only.

If a subject does not have an event (i.e., does not demonstrate clinical improvement of at least 2 points) on or before Day 28 and does not withdraw or become lost to follow up from the study on or prior to Day 28, the data will be censored at Day 28. If a subject does not have an event but withdraws from the study or is lost to follow up on or prior to Day 28, the data will be censored at the last date known that the subject has not demonstrated clinical improvement of at least 2 points up to Day 28.

If a subject does not have an event and dies before Day 28, they will be censored at Day 28.

The following additional exploratory efficacy endpoints that utilise the category ordinal scale will be analysed:

3.1.16.1 Time to clinical improvement of at least 2 points (from randomization) on a 9-point category ordinal scale, live discharge from hospital, or considered fit for discharge, whichever comes first) through Day 28

This is defined as the time (in days) from randomization to the earliest date at which any of the following criteria are met:

- First demonstrated clinical improvement of at least 2 points (i.e., a decline of two points) on the following 9-point category ordinal scale
- Live discharge from hospital

- The date the subject is considered fit for discharge (a score of 0, 1 or 2 on the ordinal scale)

The first demonstrated clinical improvement of at least 2 points and observing a score of 0, 1 or 2 (i.e. the subject is considered fit for discharge) will be determined using the same ordinal scale described in Section 3.1.16. The date of live discharge from hospital will be captured in the CHCSS page in the eCRF.

If a subject does not have an event (i.e., does not demonstrate clinical improvement of at least 2 points or is not discharged from the hospital or is not considered fit for discharge) on or before Day 28 and does not withdraw or become lost to follow up from the study on or prior to Day 28, the data will be censored at Day 28. If a subject does not have an event but withdraws from the study or is lost to follow up on or prior to Day 28, the data will be censored at the last date known that the subject did not demonstrate any of the three above criteria up to Day 28.

If a subject does not have an event and dies on or before Day 28, they will be censored at Day 28.

3.1.16.2 Time to recovery (from randomization) through Day 28

This is defined as the time (in days) from randomization to recovery, where the date of recovery is defined as the earliest date any of the categories in the following 3-point scale are met:

1. Hospitalized not requiring supplemental oxygen, not requiring medical care
2. Not hospitalized but limitations on activities
3. Not hospitalized and no limitations

Table 5 outlines how the 3-point scale will be derived from the information collected from the 9-point category ordinal scale (Section 3.1.16) and hospitalization details.

Table 5 Derivation of the 3-point scale

3-point scale	Derivation from 9-point category scale and hospitalization details
(1) Hospitalized not requiring supplemental oxygen	Hospitalized with a score of 0, 1, 2 or 3 and “Is hospitalization clinically indicated” answered No in the eCRF.
(2) Not hospitalized but limitations on activities	Discharged from hospital with a score of 2
(3) Not hospitalized and no limitations	Discharged from hospital with a score of 0 or 1

If a subject does not have an event (i.e., does not meet any of the criteria specified in the 3-point scale) on or before Day 28 and does not withdraw or become lost to follow up from the study on or prior to Day 28, the data will be censored at Day 28. If a subject does not have an event but withdraws from the study or is lost to follow up on or prior to Day 28, the data will be censored at the last date known that the subject did not meet any of the criteria specified in the 3-point scale up to Day 28.

If a subject does not have an event and dies before Day 28, they will be censored at Day 28.

3.1.17 Time to SpO₂ > 94% on room air

This is defined as the time (in days) from randomization to the first occurrence that SpO₂ > 94% on room air (i.e. not receiving supplementary oxygen) through Day 28. SpO₂ will be captured on the VS module in the eCRF.

Baseline SpO₂ is defined as the result obtained on the date of randomization (Day 1). Subjects with SpO₂ > 94% on room air at baseline will not be included in any analyses of time to SpO₂ > 94% on room air.

If a subject does not experience an event (i.e., does not have SpO₂ > 94% on room air) on or before Day 28 and does not withdraw or become lost to follow up from the study on or prior to Day 28, the data will be censored at Day 28. If a subject does not have an event but withdraws from the study or is lost to follow up on or prior to Day 28, the data will be censored at the last date known that the subject did not have SpO₂ > 94% up to Day 28.

If a subject does not have an event and dies on or before Day 28, they will be censored at Day 28.

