5.1 Inclusion Criteria

Subjects are eligible to be included in the study only if **all** of the criteria below apply.

- 1. Ability to understand the purpose and risks of the study and provide signed and dated informed consent or have a legal representative provide consent and authorization to use protected health information (in accordance with national and local patient privacy regulations).
- 2. Men and women ≥18 years of age at the time of signing the Informed Consent Form (ICF).
- 3. SARS-CoV-2 confirmed per World Health Organization criteria (including positive nucleic acid test of any specimen [eg, respiratory, blood, urine, stool, or other bodily fluid]) within 7 days of randomization.
- 4. COVID-19 pneumonia (documented radiographically) requiring hospitalization and oxygen saturation <94% on room air or requires supplemental oxygen.
- 5. Able to swallow pills.
- 6. Willing to follow contraception guidelines (refer to Appendix F).

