- Baseline is defined as the result obtained on the day of randomization (Day 1) only. Applies to:
 - Respiratory failure status at baseline
 - Baseline oxygen saturation (SpO₂)
 - Baseline for all oxygen and mechanical ventilation assessments
 - Baseline ordinal scale score
 - Baseline mSOFA score
- For all summaries, change from baseline variables will be calculated as the post-baseline value minus the value at baseline. The percentage change from baseline will be calculated as $((\text{post-baseline value} - \text{baseline value}) / \text{baseline value}) \times 100$.
- Unless stated otherwise, visit windows will apply as follows:
 - Day 1 (date of randomization): No window unless specified above (where latest result prior to date of randomization can be used)
 - Days 2-10 or discharge (whichever occurs first): no visit window. Note: if a subject is discharged prior to Day 7 they will visit the site for an assessment 2 to 4 days after discharge. Assessments should match those for Day 10.

- Day 14: ± 2 days
- Day 28: ± 3 days
- Arm 1 Safety follow-up at 28 days after last dose of acalabrutinib: ± 3 days
- Arm 2 Safety follow-up (for AEs, concomitant medications and survival assessment) at 38 days after randomization: ± 3 days
- Long-term follow-up 90 days after randomization: ± 7 days
- Observations recorded on the date closest to the scheduled assessment day (as long as this is within the visit window) will be used as the scheduled assessment. If Any observations recorded outside of the visit window will be considered unscheduled visit observations and will not be included in visit-based summaries at a treatment-group level. If multiple observations are recorded per day, or observations within a visit window are equidistant from the target day, the worst assessment reported will be used as the scheduled assessment. For laboratory and vital signs assessments, this is the maximum reported value.
- Visit-based summaries will include: Baseline (Day 1), Day 2-10, Day 14 and Day 28 where applicable, as per SoA.
- For listings at a subject level, all values will be included (regardless of whether they appear in a corresponding visit-based summary) when deriving a patient level statistic such as a maximum.

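### The drop-out censoring sentence for time to SpO₂ above 94% on room air leaves out the room-air condition, so read literally it can censor a subject still on oxygen before the last event-free assessment

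*SAP*

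**What the plan says.** SAP 3.1.17 measures time from randomization to "the first occurrence that SpO₂ > 94% on room air (i.e. not receiving supplementary oxygen) through Day 28". The room-air condition is carried into two further rules in that section:

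- Baseline exclusion: "Subjects with SpO₂ > 94% on room air at baseline will not be included in any analyses".
- Completers, who are censored at Day 28: "If a subject does not experience an event (i.e., does not have SpO₂ > 94% on room air) on or before Day 28".

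The rule for subjects who have no event but withdraw or are lost on or before Day 28 does not carry it: "the data will be censored at the last date known that the subject did not have SpO₂ > 94% up to Day 28". Deaths have their own sentence: "If a subject does not have an event and dies on or before Day 28, they will be censored at Day 28".

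No other text supplies the missing condition. SAP 4.3.2.16 refers back to 3.1.17 for withdrawals, losses and deaths, and Protocol 9.6.2 gives no censoring rule for this endpoint.

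**The concern.** An event needs two things on the same occasion: saturation above 94% and no supplemental oxygen. A subject at 96% on a nasal cannula has therefore not had the event and is known not to have had it. The drop-out sentence tests saturation alone, so it does not recognise that day as event-free.

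Such subjects can be in the analysis. Protocol 5.1 admits patients with "oxygen saturation <94% on room air or requires supplemental oxygen", and the baseline exclusion removes only those above 94% on room air. A subject above 94% on oxygen at baseline stays in.

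What is at stake is follow-up time from living drop-outs who still need oxygen. If they leave the risk set early, later risk sets are too small and the estimated rate of reaching the event is too high. If such drop-out were unequal between arms, the hazard ratio would also be affected.

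**Working it through.** The plan states no figure for this endpoint, so there is none to reproduce. The check applies the rule to example records and then sizes the effect under stated assumptions.

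**Step 1: the two rules on one record.** Take a hypothetical subject on oxygen throughout, last assessed at drop-out on Day 12, with no event.

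- Literal rule: last day on which SpO₂ > 94% is false.
- Intended rule: last day on which (SpO₂ > 94% and room air) is false.

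| SpO₂ pattern, always on oxygen | Literal | Intended |
|---|---|---|
| Above 94% on every day | no qualifying date from Day 1 on | Day 12 |
| 93% on Day 1, then 96% | Day 1 | Day 12 |
| 93% on Days 1 to 3, then 96% | Day 3 | Day 12 |
| 96%, one reading of 93% on Day 8 | Day 8 | Day 12 |
| 96%, then 93% on the last day | Day 12 | Day 12 |

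The loss runs from nothing to the whole follow-up, depending on when the last low reading falls. Where several readings exist on one day, SAP 4.1 takes the worst for the scheduled assessment and adds: "For laboratory and vital signs assessments, this is the maximum reported value". If that rule is applied here, a same-day dip to 94% or below would be hidden and the literal date could move earlier still.

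**Step 2: comparison with neighbouring endpoints.** SAP 3.1.16, on the ordinal scale, uses its full event definition for drop-outs: "the data will be censored at the last date known that the subject has not demonstrated clinical improvement of at least 2 points". SAP 3.1.8, 3.1.16.1 and 3.1.16.2 likewise censor at the last date known to be without the event as defined. Only 3.1.17 tests part of its event.

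**Step 3: illustrative size.** SAP 1.3 reports 62 randomized, so about 31 per arm. The other inputs are assumptions:

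- a constant hazard, with 60% or 80% reaching the event by Day 28;
- k subjects in one arm assigned a drop-out day between Day 5 and Day 20;
- those without an event by that day moved to Day 1, the worst pattern in Step 1;
- 4,000 runs per setting.

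Average rise in the Day 28 Kaplan-Meier estimate, in percentage points:

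| k | 60% by Day 28 | 80% by Day 28 |
|---|---|---|
| 1 | 0.40 | 0.30 |
| 2 | 0.79 | 0.61 |
| 3 | 1.23 | 0.93 |
| 5 | 2.18 | 1.62 |

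The largest shift in any single run was 8.7 points (k = 5, 60%).

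Some of the k subjects reach the event before their drop-out day and are not moved. At the mean drop-out day of 12.5, the share still without an event is 0.4^(12.5/28) = 0.66 or 0.2^(12.5/28) = 0.49. For k = 5, the shift per subject actually moved is 2.18/(5 × 0.66) = 0.66 or 1.62/(5 × 0.49) = 0.66 points. For k = 1 it is 0.40/0.66 = 0.61 or 0.30/0.49 = 0.61. Each subject moved to Day 1 therefore costs about 0.6 to 0.7 points, and five subjects actually moved would cost about 3.

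**The case against.** The best defence is that the sentence is shorthand. The section title, the event definition, the baseline exclusion and the sentence immediately before it all say room air. The drop-out sentence itself opens with subjects who have no event, a term already defined. The parallel endpoints point the same way, and a careful programmer would probably supply the missing words. This stands as a reason to rate the point low: the documents do not show that a wrong derivation was intended or made. It does not remove the inconsistency. SpO₂ is recorded on the VS form and oxygen use on the OXYGEN and VENTUSE forms (SAP 3.1.17 and 3.2.6), so the literal date can be derived from VS alone without any check of oxygen use.

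The affected group is also narrow: no event, withdrawal or loss by Day 28, and above 94% on oxygen at the last assessment. The endpoint is one of many secondary ones, and Protocol 9.1 states that there is no formal hypothesis testing. All of this stands.

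A reader might infer more than the documents support:

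- **That affected subjects are generally censored near Day 1.** This needs every later reading to be above 94%; Step 1 shows other outcomes.
- **That most of the trial is exposed.** Protocol 5.1 gives two alternative routes to eligibility and no proportions.
- **That a large share of an arm's follow-up is lost.** Suppose 3 to 6 subjects lose 8 to 9 days each, or 24 to 54 subject-days. Against 31 × 10 = 310 subject-days that is 8% to 17%. But this puts every assumed drop-out in one arm, and the 10-day mean has no source. With 60% or 80% reaching the event by Day 28 at a constant hazard λ, the mean time at risk is (proportion reaching the event)/λ. That is 0.6/0.0327 = 18.3 or 0.8/0.0575 = 13.9 days. The share becomes 24/(31 × 18.3) = 4% to 54/(31 × 13.9) = 13%, still with all drop-outs in one arm.
- **That the hazard ratio is biased.** This needs drop-out on oxygen to differ by arm. That is possible in an open-label trial, but the documents do not show it.

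**Conclusion.** The sentence is wrong as written, and the point is minor. Followed literally, it can censor a subject who leaves while above 94% on oxygen before the last assessment at which that subject is known to be event-free. The direction is a slight overstatement of the rate of reaching the event.

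The size depends on how many subjects drop out in this state, which the documents do not say. The simulated average rise of about 0.3 to 2.2 percentage points in the Day 28 estimate rests on 1 to 5 assigned drop-outs in an arm of 31, a constant hazard, and the worst-case move to Day 1. With later low readings the shift would be smaller, and with no such drop-outs it is zero.

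**What to change.** In SAP 3.1.17, restore the room-air condition in the drop-out sentence: censor at the last date, up to Day 28, on which the subject is known not to have had SpO₂ above 94% while on room air. Add that an assessed day on supplemental oxygen or ventilation counts as event-free whatever the SpO₂.

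The cost is one phrase, one clarifying sentence and the matching derivation. No new data are needed, because SAP 3.2.6 already identifies days with no oxygen or ventilation reported. The SAP amendment history records earlier corrections to withdrawal and loss-to-follow-up wording as typos, so this would be a change of the same kind.

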3.2 Safety variables

The safety of acalabrutinib in subjects with COVID-19 when administered with BSC is a primary endpoint and will be assessed by type, frequency, severity, and relationship to study treatment of any treatment-emergent adverse events (TEAEs) or abnormalities of laboratory tests, serious adverse events (SAEs), or adverse events leading to discontinuation of study treatment.

3.2.1 Adverse events

After the signing of the ICF, all SAEs must be reported. After the first dose of study treatment, all AEs/SAEs, irrespective of attribution of causality, must be reported. AE reporting, irrespective of seriousness, ends 28 (± 3) days after the last dose of study treatments(s) for those on acalabrutinib + BSC (Arm 1) and 38 (± 3) days from randomization for those on BSC only (Arm 2).

The following are NOT considered an AE:

- **Pre-existing condition that has not worsened:** A pre-existing condition (documented on the medical history eCRF) is not considered an AE unless the severity, frequency, or character of the event worsens during the study period.
- **Diagnostic testing and procedures:** Testing and procedures should not be reported as AEs or SAEs, but rather the cause for the test or procedure should be reported. If a test or procedure is done to rule out a diagnosis, the sign or symptom leading to the test/procedure should be the event term, and the event term should only be updated to the diagnosis if/when the diagnosis is confirmed. Testing and procedures performed solely as screening measures (e.g., routine screening mammography or colonoscopy) should not be reported as AEs or SAEs.
- **Abnormal laboratory results:** Abnormal laboratory results are not AEs unless they are clinically significant. For example, a clinically significant laboratory result is one that requires treatment (for example a blood transfusion for low haemoglobin) or requires a change in study drug (e.g., lowering the dose or withholding study drug while the laboratory finding resolves or stabilizes).
- **Progression of underlying disease:** Progression of underlying disease unequivocally related to COVID-19 pneumonia (such as worsening of respiratory status or complications associated with pneumonia) will not be reported as an AE if it is clearly consistent with the suspected progression of the underlying disease. Clinical symptoms of progression may be reported as AEs if the symptoms cannot be determined as exclusively due to the progression of the underlying disease, or if

Events will be defined as treatment-emergent if they onset, or worsen (by investigator report of a change in intensity), during the treatment period as defined in the CSP. The Medical Dictionary for Regulatory Activities (MedDRA) (using the latest or current MedDRA version) will be used to code the AEs. AEs will be graded according to the National Cancer Institute Common Terminology Criteria for AEs (CTCAE) version 5.0. The CTCAE grade will be assigned by the investigator as follows:

- Grade 1: Mild AE
- Grade 2: Moderate AE
- Grade 3: Severe AE
- Grade 4: Life-threatening or disabling AE
- Grade 5: Death related to AE

For events with varying severity, the worst reported grade will be used.

Missing start and stop dates for AEs will be handled using the rules described in Section 4.1.

